
Analysis: Observed toxicities will be summarized in terms of type (organ affected or laboratory determination), severity, attribution, time of onset, duration, serum concentration of the active leflunomide metabolite, probable association with the study treatment and reversibility or outcome. Baseline information (e.g. the extent/type of prior therapy) and demographic information will be presented as well to describe the patients treated in this study.
 
Rates and 95% Clopper Pearson binomial confidence interval (CI) will be calculated for overall response rate (patients that have confirmed sCR/CR/VGPR or PR) and clinical benefit rate (patients that have confirmed sCR/CR/VGPR/PR/MR or SD). In addition, sub-analyses will be performed where participants will be considered evaluable for response if they are confirmed eligible, receive at least 75% of leflunomide during the first cycle of therapy and have their disease re-evaluated. Response rates will also be explored based on number/type of prior therapy(ies) and serum concentration of the leflunomide metabolite (μg/mL). Time to response and survival will be estimated using the product-limit method of Kaplan and Meier.
 
Serum trough levels of leflunomide's active metabolite, teriflunomide (A77 1726), will be measured in each patient at multiple time points throughout the study. Both total and free teriflunomide will be tested. The association between serum levels and toxicity, as well as response, will be evaluated at the conclusion of the study.
 
Genetic polymorphisms in genes associated with the biological activity of leflunomide (e.g., DHODH, CYP1A2, and CYP2C19) have been previously described and will be explored for possible associations with response and safety outcomes.
 
Ex vivo studies will be performed on bone marrow aspirate-derived cells to evaluate the IC50 for teriflunomide and the potential synergy with other anti-neoplastic agents. Correlation analyses will be performed to determine the relationship between ex vivo and in vivo response.
 
Preliminary molecular profiles for miRNA, mRNA, and DNA methylation status will be derived from both ex vivo and in vivo treatment. These profiles will be used to identify molecular correlates of therapeutic response using pathway identification and supervised principal components analysis.

Sponsor/Licensee:
Investigator Initiated: City of Hope
Case Report Forms

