11.2 Phase II/Primary Endpoint: Response

The primary endpoint is response. Response will be categorized using the IMWG response criteria for multiple myeloma [37, 38]. Table 11.2 summarizes the categories and criteria.

Table 11.2 Response Criteria

Response Category	Response Criteria
Complete response (CR)*	Negative immunofixation of serum & urine, AND Disappearance of any soft tissue plasmacytomas, AND < 5% plasma cells in bone marrow
Stringent complete response (sCR)*	CR (as defined above) PLUS: Normal FLC ratio, AND Absence of clonal cells in bone marrow by immunohistochemistry or immunofluorescence
Very good partial response (VGPR)**	Serum and urine M-component detectable by immunofixation but not on electrophoresis, OR ≥ 90% reduction in serum M-component plus urine M-component < 100mg per 24h
Partial response (PR)**	≥ 50% reduction of serum M protein and reduction in 24h urinary M protein by ≥ 90% or to < 200mg per 24h If serum and urine M protein are unmeasurable, a ≥ 50% decrease in the difference between involved and unininvolved FLC levels is required in place of the M protein response criteria If serum and urine M protein are unmeasurable, AND serum free light assay is also unmeasurable, a ≥ 50% reduction in bone marrow plasma cells is required in place of M protein, provided baseline percentage was ≥ 30%. In addition to the above criteria, if present at baseline, ≥ 50% reduction in the size of soft tissue plasmacytomas is also required
Minimal Response	• 25% but ≤ 49% reduction of serum M protein and reduction in 24-hour urine M-protein by 50 to 89% which still exceeds 200 mg per 24 hr

Response Category	Response Criteria
(MR)**, ***	
 In addition to the above criteria, if present at baseline, 25-49% reduction in the size of soft tissue plasmacytomas is also required No increase in size or number of lytic bone lesions (development of compression fracture does not exclude response)
Stable disease (SD)**	Not meeting criteria for CR, VGPR, PR, or PD

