13.2 Evaluable Participants and Participant Replacement

All participants will be evaluable for toxicity from the time of their first treatment with leflunomide.

Evaluable for Dose-Escalation/De-Escalation Criteria: Participants will be considered evaluable for dose-escalation criteria if they receive at least 75% of leflunomide and are followed during cycle 1, or experience a DLT. All participants who are not evaluable for dose-escalation criteria will be replaced. Note: While patients who receive <75% of the intended dose of leflunomide will be considered unevaluable for determination of MTD, if a patient discontinues leflunomide due to toxicities prior to receiving 75% of the dose, the patient will be considered evaluable and will not be replaced.

Evaluable for Response: Participants will have their response classified according to the IMWG response criteria (See [Section 11](#)). All patients included in the study will be assessed for response to treatment, even if there are protocol treatment deviations or if the patient is later determined to be ineligible. Each patient will be assigned one of the following categories: 1) complete response (CR), 2) stringent complete response (sCR), 3) very good partial response (VGPR), 4) partial response (PR), 5) minimal response (MR), 6) stable disease (SD), 7) progressive disease (PD), 8) early death from malignant disease, 9) early death from toxicity, 10) early death due to other cause, or 11) unknown (not assessable, insufficient data).

All of the patients who met the eligibility criteria (with the possible exception of those who received no study medication) should be included in initial analysis of response rate; overall response (sCR/CR/VGPR or PR) and clinical benefit response (sCR/CR/VGPR/PR/MR or SD). Patients in response

categories 7-11 should be considered to have a treatment failure. Thus, an incorrect treatment schedule or incorrect drug administration does not result in the exclusion from the analysis of the response rate.

In addition, as part of the phase II anti-myeloma activity assessment, a sub-analysis will be performed where participants will be considered evaluable for response if they are confirmed eligible, receive at least 75% of leflunomide during the first cycle of therapy and have had their disease re-evaluated (phase II primary endpoint).

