13.5 Statistical Analysis Plan

Patient demographic and baseline characteristics, including age, gender, medical history, and prior therapy, will be summarized using descriptive statistics. For continuous variables, descriptive statistics (number [n], mean, standard deviation, standard error, median (range) will be provided. For categorical variables, patient counts and percentages will be provided.

Analysis: Observed toxicities will be summarized, for all dose levels, in terms of type (organ affected or laboratory determination), severity, time of onset, duration, serum concentration of the active leflunomide metabolite, probable association with the study treatment and reversibility or outcome.

The overall response rate and clinical benefit response rate will be calculated, for the initial and sub-analysis for all dose levels; Clopper Pearson binomial 95% confidence intervals will be calculated for these estimates. As part of the initial analysis of response, the overall response rate (patients that have confirmed sCR/CR/VGPR or PR) and clinical benefit response rate (patients that have confirmed sCR/CR/VGPR/PR/MR or SD) will be calculated among all patients included in the study even if there are

protocol treatment deviations or if the patient is later determined to be ineligible. In addition, as part of the phase II anti-myeloma activity assessment, sub-analyses will be performed where participants will be considered evaluable for response if they are confirmed eligible, receive at least 75% of leflunomide during the first cycle of therapy and have their disease re-evaluated. Response rates will also be evaluated based on number/type of prior therapy(ies) and serum concentration of the leflunomide metabolite (μ g/mL). Time to response and survival will be estimated using the product-limit method of Kaplan and Meier.

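### Section 13.2 puts the phase II primary-endpoint label on an evaluable-only sub-analysis, and no section unambiguously names the patient set for the primary ORR and the Simon rules

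*Combined protocol and SAP*

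**What the plan says.** **Primary endpoint.** Section 11.2 says "The primary endpoint is response. Response will be categorized using the IMWG response criteria for multiple myeloma". It gives no analysis set.

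**Initial analysis, section 13.2.** Every patient in the study is assessed for response "even if there are protocol treatment deviations or if the patient is later determined to be ineligible". The next paragraph is narrower: "All of the patients who met the eligibility criteria (with the possible exception of those who received no study medication) should be included" in the initial analysis of response rate. Patients in "categories 7-11 should be considered to have a treatment failure"; these categories are progression, the three kinds of early death, and unknown. The section adds that "incorrect drug administration does not result in the exclusion from the analysis of the response rate".

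**Sub-analysis, section 13.2.** A further analysis is restricted to confirmed-eligible patients who "receive at least 75% of leflunomide during the first cycle of therapy and have had their disease re-evaluated (phase II primary endpoint"). The parenthesis closes the sentence.

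**The same sub-analysis elsewhere.** The synopsis (Statistical Considerations) says "In addition, sub-analyses will be performed where participants will be considered evaluable for response if they are confirmed eligible", with the same dosing and re-evaluation conditions and no primary label. Section 13.5 is equivalent, also without the label. It runs the initial analysis in all patients included, naming those later found ineligible, and says "The overall response rate and clinical benefit response rate will be calculated, for the initial and sub-analysis for all dose levels".

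**Simon rules, section 13.3.** Stage 1 enters 19 patients and stops at 3 or fewer responses. Stage 2 enters 20 more, and 9 or more responses among 39 is positive. The 6 phase I patients treated at the RP2D are part of this group. Section 5.4 speaks of up to 39 patients treated.

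**The concern.** A single-arm trial with a response-rate endpoint needs one pre-specified denominator. The only place where these documents join a patient set to the words primary endpoint is a sub-analysis defined by what happens after treatment starts: how much cycle 1 drug was taken, and whether disease was re-assessed. Patients who fail those conditions are likely to be mostly non-responders, and the rest of section 13.2 keeps them in the response-rate analysis.

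Setting the parenthesis aside does not fully settle the matter, because sections 13.2 and 13.5 describe the fallback set differently for patients later found ineligible. What is at stake is the headline ORR and its confidence interval against the 30% target. In an open-label trial, the choice between two reported rates could be made after the results are known.

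**Working it through.** **1. The plan's own design.** Inputs from section 13.3: null ORR 0.15, target 0.30, n1 = 19, r1 = 3, n = 39, r = 8. With X1 ~ Bin(19, p) and X2 ~ Bin(20, p):

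- P(early stop) = P(X1 ≤ 3) = 0.684 at p = 0.15 (stated: 0.68).
- P(positive) = Σ over x = 4 to 19 of P(X1 = x) · P(X2 ≥ 9 − x) = 0.0974 at p = 0.15 and 0.8029 at p = 0.30 (stated limits: 0.10 and 80%).

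The design reproduces and is not in question.

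**2. The candidate sets side by side.**

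| Place | Label | Later-ineligible patients | Under-dosed or not re-evaluated |
|---|---|---|---|
| 13.2, initial analysis | initial | worded as those meeting eligibility | kept; unknown counts as failure |
| 13.5, initial analysis | initial | included | kept |
| 13.2, sub-analysis | additional, with primary-endpoint parenthesis | excluded | excluded |
| Synopsis and 13.5, sub-analysis | additional, no parenthesis | excluded | excluded |

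Sections 13.3 and 5.4 give accrual counts (entered, treated), not an analysis set.

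**3. Effect on the reported rate.** The documents give no exclusion rate, so the numbers excluded are assumed. Take 39 entered and 9 responders, with Clopper-Pearson 95% intervals:

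| Excluded (assumed) | ORR | 95% CI |
|---|---|---|
| none | 9/39 = 23.1% | 11.1 to 39.3 |
| 4 non-responders | 9/35 = 25.7% | 12.5 to 43.3 |
| 8 non-responders | 9/31 = 29.0% | 14.2 to 48.0 |
| 3 non-responders and 1 responder | 8/35 = 22.9% | 10.4 to 40.1 |

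The upward shift depends on the excluded patients being mostly non-responders. One responder among four removes it.

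**4. Effect on the decision.** The rules compare a count of responders with 3 and 8. If 19 and 39 are patients entered and the cut-offs stay, excluding non-responders leaves the count, the decision and alpha (0.097) as they were. The decision can change only if a responder lies outside the set at a boundary:

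- P(exactly 4 of 19) = 0.171 at ORR 15% and 0.149 at 30%.
- P(pass stage 1 and exactly 9 of 39) = 0.047 and 0.070.

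These bound the opportunity; an actual change is rarer. Suppose each responder has an assumed chance q of lying outside the set. Responses counted in the set then occur at rate p(1 − q), and a positive result in the set implies a positive result in all patients. So P(positive in all, negative in the set) = P(positive at p) − P(positive at p(1 − q)):

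| ORR | q = 2% | q = 5% |
|---|---|---|
| 15% | 0.0974 − 0.0884 = 0.9% | 0.0974 − 0.0759 = 2.2% |
| 30% | 0.8029 − 0.7825 = 2.0% | 0.8029 − 0.7493 = 5.4% |

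**The case against.** The benign reading of the parenthesis is the more natural one. The sentence opens as an addition and calls the set a sub-analysis, the parallel texts carry no label, and the synopsis and section 11.2 say the phase II primary endpoint is response. The parenthesis may therefore only note which endpoint the sub-analysis concerns. The initial analysis, the treatment-failure rule and the counts of patients entered and treated together point to an all-treated denominator. Both rates are reported with intervals, so nothing is hidden. A confirmed responder has already been re-evaluated, so only the dosing or eligibility condition could remove one, and eligibility is verified centrally before registration (section 4.3).

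Most of this stands, and it limits the point to ambiguous labelling of the reported rate. It does not supply the missing sentence that names the set, and it does not reconcile sections 13.2 and 13.5 on ineligible patients.

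A reader might also infer more than the documents support:

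- **That the sub-analysis drops every early death.** A patient who took 75% of cycle 1 drug, was re-evaluated and then died is not excluded by those words.
- **That the all-dose-level rate in section 13.5 is a rival primary set.** It is a descriptive rate for the whole trial; section 13.3 describes the phase II group separately.
- **That alpha is inflated.** This would need 19 and 39 to be evaluable patients, with unevaluable non-responders replaced. The chance of a positive trial at an all-treated ORR of 15% would then be 0.157 with an assumed 10% unevaluable and 0.252 with 20%. Section 13.2 provides replacement only for dose-escalation evaluability, and section 13.3 counts patients entered.

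**Conclusion.** The point holds as conflicting text about the primary denominator, and should be fixed. The 13.2 parenthesis can be read as making a post-baseline-selected set primary. The parallel texts do not support that reading, but no section rules it out explicitly. The two descriptions of the initial analysis also differ on patients later found ineligible.

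The size is modest. The reported ORR might rise by about 3 points with 4 non-responders excluded, or 6 with 8, on an outcome of 9 responders; the direction is probable, not certain. On the stated counts and cut-offs there is no effect on alpha or the decision from dropping non-responders. The chance of a changed decision is about 1% to 5% under the assumed 2% to 5% loss of responders. The exclusion numbers and loss rates are assumptions. Confidence is medium, because the benign reading may be what was meant.

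**What to change.** - In section 13.2, delete the parenthetical primary-endpoint label from the sub-analysis and keep that set as supportive.
- In sections 13.2, 13.3 and 13.5, state that the primary ORR and both Simon rules (stop at 3 or fewer of 19; not warranted at 8 or fewer of 39) use all treated patients counted toward the 39, including the phase I patients at the RP2D, with categories 7 to 11 as non-responders.
- Align section 13.2 with section 13.5 so that both include patients later found ineligible in the initial analysis.

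The cost is a short amendment to three sections and a possibly slightly lower reported primary ORR. Sample size, cut-offs, alpha and power do not change.

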13.3 Study Design

13.3.1 Phase I Design

This single agent phase I dose-escalation trial is designed to determine the MTD and RP2D. The RP2D of leflunomide will generally be the MTD, but it may be less than the MTD based on a review of available data/cumulative toxicities. Extensive pharmacokinetic and pharmacodynamic studies are also incorporated into this protocol and may be helpful in determining the RP2D.

While the standard dose of leflunomide, 20mg daily, is FDA approved for continuous treatment of rheumatoid arthritis, leflunomide has been administered without an increase in the type, frequency or severity of adverse events at doses up to 40 mg/day in patients with Wegner's granulomatosis, and up to 60mg/day in a subset of patients with polyoma BK neuropathy to achieve targeted therapeutic levels. We will therefore attempt to escalate the dose of leflunomide to three times that approved for RA using a modified rolling six dose-escalation/ de-escalation/expansion design, a more conservative version of the rolling six design of Skolnik, et al.[1]. The starting dose of leflunomide is 20mg daily, with the intention to test up to 60mg daily. Escalation will proceed in increments of 20mg/day (odd numbered dose levels); de-escalation will proceed in decrements of 10mg/day.

Table 13.3.1 Dose Levels

Dose Level	Leflunomide Dose*
-1	10 mg PO daily
1	20 mg PO daily
2	30 mg PO daily
3	40 mg PO daily
4	50 mg PO daily
5	60 mg PO daily

*NOTE: Leflunomide is administered with a loading dose of 100 mg for the 1st three doses.

13.3.2 Phase I Dose Escalation

This phase I trial will employ a modified rolling six design, a more conservative version of the rolling 6 design of Skolnik, et al [1]. In this design, at most 3 patients will be under observation for DLT (in cycle 1) on the current test dose level at any time. Patients who are not evaluable for dose escalation will be replaced. Once each patient completes cycle 1 and passes without a DLT, an additional patient *may* be accrued on that dose level for up to 6 patients. Once 3 patients have completed cycle 1 with no patient at that dose level experiencing a DLT, the dose can be escalated. Up to 3 additional patients may be treated at the current dose level. Although this design does not require that 6 patients be treated, no more than 6 evaluable patients will be accrued to any dose level during the dose finding portion of this study. If at any time, the dose level has 1 documented DLT with fewer than 6 evaluable patients, accrual will continue until 6 patients are evaluable. Escalation will terminate as soon as two or more patients

experience a DLT attributable to the study treatment. MTD will be the highest dose in which $\leq 1/6$ patients experience a DLT. There will be no dose escalation within a patient. These rules are outlined in Table 13.3.2.

Table 13.3.2: Dose Escalation Rules

With DLT [^]	# Patients on Current Level		Action
	Evaluable	Evaluable + At Risk [^]	
0	0	1-2	Accrue next patient at this level*
0	0	3	Hold accrual
0	1	1-3	Accrue next patient at this level
0	1	4	Hold accrual
0	2	2-4	Accrue next patient at this level
0	2	5	Hold accrual
0	3-6	3-6	Accrue next patient at the next higher level* ^{*,+}
1	1	1-2	Accrue next patient at this level
1	1	3	Hold Accrual
1	2	2	Accrue next patient at this level
1	2	3-4	Hold accrual
1	3-5	3-5	Accrue next patient at this level
1	3-5	6	Hold accrual
1	6	6	Accrue next patient at the next higher level*
2**	any	any	Accrue next patient at next lower level (max 6)

[^]: DLT: a patient with a documented DLT
 Evaluable: a patient who is either fully evaluable for toxicity for the purpose of dose escalations or has a DLT
 At Risk: a patient who is on treatment and has not yet passed the evaluation period nor had a DLT
^{*}: During the dose-escalation portion, if higher dose level is already closed, the next lower dose will accrue to a total of 6 patients, with 2 or higher DLTs requiring further dose de-escalation.
⁺: Although under this scenario escalating to the next higher dose level is suggested, additional patients can be accrued to the current level -up to n=6 patients.
^{**}: Patients treated on a higher dose will have their treatment modified to the dose below the dose level with 2 DLTs, if pending patients have DLT.

Phase II Design

Following completion of the phase I portion of the study and identification of the RP2D, the phase II portion of the study will be initiated. Recent studies evaluating daratumumab, a CD38 monoclonal antibody, as monotherapy for relapsed/refractory multiple myeloma were recently published [39, 40] and have led to FDA approval of this agent. One study included patients with relapsed multiple myeloma treated with at least three lines of therapy while the other included patients treated with at least two prior lines of treatment. Treatment with daratumumab as a single agent lead to an overall response rate of 29.2% and 36% respectively in each of these studies. In both studies, the agent investigated was well tolerated but required IV dosing once weekly for 8 doses, followed by twice-monthly doses for 8 doses and then monthly thereafter. We suspect leflunomide to be similarly well tolerated but with a more convenient dosing schedule. Because we are including patients who have received at least three prior lines of treatment, we will target an overall response rate of 30% for the phase II portion of the study.

This single-center, single arm phase II trial will implement a Simon Two-Stage Optimal Design [2, 3]. to evaluate the anti-myeloma activity of leflunomide, when given as a single agent, as assessed by overall response rate (ORR), in patients with relapsed or relapsed/refractory MM. The phase II portion of the study is expected to enroll a minimum of 19 and a maximum of 39 patients. The sample size is based on the desire to discriminate a promising ORR of 30% from a disappointing response rate of 15% using a type I error rate of 0.10 and power of 80%.

At stage 1, 19 patients will be entered on the study. If ≤ 3 responses are seen, the study will be terminated. If at least 4 patients achieve response, the trial will continue to the second stage. The 6 patients treated at the RP2D in the phase I portion will be evaluated as part of this phase II group. The probability of early stopping after the first stage is 0.68.

At stage 2, 20 additional patients will be entered. At the end of stage 2, if 9 or more patients respond, leflunomide -as single agent therapy, will be considered worthy of further study. If ≤ 8 patients respond further investigation is not warranted.

